Researchers in the stroke motor-recovery literature have controlled for the potential paradoxical effect of 1 Hz rTMS by first administering a 6 Hz rTMS pulse sequence. In contrast to slow rTMS, pulse sequences above 5 Hz have an excitatory effect [37]. This excitatory pulse sequence in essence “primes” the targeted brain region so that the 1Hz pulse sequence has the expected inhibitory effect, while at the same time enhancing the effect [38]. To date, only one study has applied an excitatory priming sequence to control for potential varying levels of cortical excitability in aphasia. In this study by Kakuda and colleagues [39], participants received 10 minutes of 6 Hz priming stimulation prior to 20 minutes of 1 Hz low-frequency rTMS to RH PTR every weekday for two consecutive weeks. The rTMS was followed by 60 minutes of speech-language therapy (SLT). Improvement was noted for all four participants on both receptive and expressive language measures following the series of rTMS sessions. However, this study had several critical limitations, most notably that all participants received speech-language therapy as part of the protocol. It is therefore impossible to determine the source of the measured improvements (the rTMS, the SLT, or their interaction). In addition, as all participants received the excitatory priming sequence, the study was unable to conclude whether the excitatory priming produced any additional benefit above and beyond that of the standard 1Hz rTMS protocol.

It is highly likely that pre-rTMS RH PTR excitability *would* differ between individuals with chronic aphasia depending on the extent to which it is recruited during recovery. If an individual with chronic aphasia retained some function of LH PTR, which would be expected for those individuals without left frontal lesions, they would not be expected to demonstrate a large amount of compensatory recruitment of RH PTR [28], and hence show little benefit from rTMS induced inhibition of this area. In fact, Kakuda and colleagues in a different study [40] found that the location of peak activation during functional magnetic resonance imaging (fMRI) of a repetition task was in the left hemisphere perilesional areas for over half of the participants with chronic aphasia in their study. *Therefore, it is imperative to have pre-rTMS neuroimaging measures of levels of RH PTR activation in order to accurately interpret the rTMS effects.*

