The second visit will begin with the first rTMS session (also described below) which will then be followed directly by the post-rTMS MRI scan. Starting the following day, the subsequent nine sessions will consist only of rTMS for a total of 10 rTMS sessions. The sessions in the rTMS series will take place daily across two weeks excluding weekends. A post-testing session, scheduled the week after the final rTMS session, will include an MRI scan and repeat administration of the language assessments that were administered during the screening visit. A final follow-up session, identical in design to the post-testing session, will be scheduled in an additional 7-10 weeks. All study-related evaluations will be administered by the PI (a licensed speech-language pathologist) or in Year 2 by the staff speech-language pathologist. Study participants will receive up to \$275 for time and local travel expenses and up to an additional \$1500 to defray lodging expenses incurred as part of study participation, to be pro-rated if they do not complete all study procedures (including follow-up visits).

Participants will be pseudo-randomly assigned to an rTMS treatment group (priming stimulation vs no priming stimulation) depending on the outcome of their baseline fMRI (described in C1.1, below). That is, an equal number of participants with and without baseline RH PTr activation will be approximated in each group.

C.1.1 MRI Procedure

fMRI Overt Confrontation Picture Naming Task. Images will be acquired using a 3.0 Tesla parallel-acquisition, echo-planar equipped Siemens MRI scanner. Participants will lay supine in the scanner wearing hearing protection and over-ear headphones. Their heads will be secured with foam padding to minimize movement.

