Motor Threshold and Intensity Determination. To standardize TMS stimulation intensity prior to rTMS, a resting motor evoked threshold (MT) will be established based on a distal upper extremity motor response. The MT will be measured by delivering single stimulations to the motor cortex with gradually increasing intensity no more frequently than every 3 sec, i.e. ~0.3 Hertz. Threshold is defined as the lowest intensity of stimulation producing motor evoked potentials of at least 50 μ V (or a visible movement of the digit) in 5 of 10 trials. Our standard stimulation intensity will be 90% of the MT.

Individual fMRI-based coil targeting. Evidence suggests that the degree of spatial resolution required to target specific cortical sites such as the PTr is achieved more readily when rTMS is used in conjunction with image-guided navigation techniques [48]. This stereotactic targeting also ensures more consistent coil placement across sessions. Following individual determination of stimulation intensity, coil placement individually targeted to the RH PTr will be performed using a frameless stereotactic method as described in Neggers and colleagues [49] and will be implemented in the BrainVoyagerQX software neuro-navigation package. Following coil positioning, participants will receive rTMS treatment according to their group assignment (see below).

TMS Administration.

Group A: Inhibitory only rTMS group: Inhibitory 1Hz rTMS will be applied continuously for 1200 pulses (20 minutes) 5 days per week across 2 weeks (10 sessions total).

Group B: Excitatory primed rTMS group: The inhibitory sequence described above will be preceded for each session by priming stimulation which will consist of intermittent 6-Hz rTMS applied in 5 second trains with 25 second intervals between trains for a total 600 pulses (10 minutes).

C2. Data Analysis

C2.1 Analysis of Behavioral Measures: Naming data (item-level performance on the PNT) will be used for analysis of rTMS treatment effects by group. Accuracy data will be analyzed using multilevel linear or logistic regression in R. Models will include fixed effects of session (baseline, post-treatment, follow-up), and group (Group A, Group B) and random effects of subject and item. Analyses may include additional random-effects structure if needed to improve model fit.

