Dynamic causal modeling (DCM) will be used to estimate effective connectivity changes due to inhibitory rTMS across time. Regions to be included in the DCM analysis will be derived from clusters of contiguous voxels surviving an omnibus F-test for the effect of interest (correct naming > crosshair fixation) at $p < 0.001$ uncorrected from the first-level fMRI analysis. Regions will be constrained to only include those clusters that fall within the traditionally outlined “language network” in the LH (inferior frontal lobe, temporal lobe, and portions of the inferior and posterior parietal lobe, [51]) and the corresponding RH homologues. The effective connectivity model (estimate of coupling and weights between these regions) will be estimated via post-hoc network discovery methods [52]. This method uses Bayesian model selection methods to select the model that was the most likely to have generated the time series data from all possible combinations of bi-directional connections between the regions. Coupling weights for interhemispheric connections will be summed for each participant for each scanning session. Other post-hoc analyses of the DCM results may be undertaken to explore both inter- and intra-hemispheric network level effects of the rTMS.

Finally, change in naming accuracy on the PNT across sessions will be correlated with change in LI, functional activation in RH PTr, and interhemispheric effective connectivity across sessions. A positive correlation between naming gains and 1) a left-hemisphere directed LI shift, and 2) a decrease in RH inhibition of LH (more positive RH to LH directional coupling weights) will support Hypothesis 1a and 1b, respectively. A positive correlation between the magnitude of pre-TMS RH PTr activation and 1) decrease in RH PTr activation across scan sessions, and 2) magnitude of left-hemisphere directed LI shift will support Hypothesis 2a and 2b, respectively. A significant interaction of group and session (analysis C2.1) suggesting that Group B receiving the 6 Hz primed inhibitory rTMS showed greater naming improvement across time will support Hypothesis 3.

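### The C2.1 naming model names no term for the factor used to balance the arms and leaves the by-subject session effect optional; the H1 correlations should also be tested with group as a covariate

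*Combined protocol and SAP*

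**What the plan says.** - **Allocation (C.1 Procedures).** Assignment to priming or no priming is pseudo-random and depends on the baseline fMRI, so that "an equal number of participants with and without baseline RH PTr activation will be approximated in each group".
- **Why the factor matters (A.3.1).** People who recruit RH PTr little are expected to be less active there and "hence show little benefit from rTMS induced inhibition of this area". The same section describes the one earlier aphasia study of priming as having "applied an excitatory priming sequence to control for potential varying levels of cortical excitability in aphasia".
- **Naming model (C2.1).** "Models will include fixed effects of session (baseline, post-treatment, follow-up), and group (Group A, Group B) and random effects of subject and item". The next sentence adds: "Analyses may include additional random-effects structure if needed to improve model fit". No activation term is named.
- **Hypothesis 3 (end of C2.2).** The criterion opens "A significant interaction of group and session (analysis C2.1" and requires greater improvement in Group B. The interaction is not in the C2.1 model statement.
- **Hypothesis 1 (end of C2.2).** The plan states that "change in naming accuracy on the PNT across sessions will be correlated with change in LI, functional activation in RH PTr", and with interhemispheric connectivity. No group term is named.
- **Hypothesis 2 (end of C2.2).** Support comes from "A positive correlation between the magnitude of pre-TMS RH PTr activation and 1) decrease in RH PTr activation across scan sessions", and from a correlation of that activation with the LI shift. Again no group term is named.
- **Size (Study timeline).** 6 participants in Year 1 and 10 in Year 2, so 16. Arm sizes are not given.

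**The concern.** The trial balances on a variable that it expects to predict response, then does not name it in the between-arm analysis. Balancing removes the factor's variation from the difference between arms. A model without the factor leaves that variation in the error term, so the standard error is too large and the test loses power.

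That argument applies only if the model lets participants differ in how much they change. The random effects named in C2.1 do not require this. A subject intercept absorbs stable differences in level but not differences in change. If change varies between people, the group-by-session test then treats items as the source of replication and its standard error is too small. The two gaps push in opposite directions, so the model statement needs both settled.

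For Hypothesis 1, a correlation over both arms mixes two sources: association between participants within an arm, and the difference between arms. If priming moves naming and imaging together, the second source alone can produce a positive correlation. It would not show that the participants with larger imaging change are those who gain more.

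**Working it through.** The available text gives no SD, effect size, power or significance level for these tests, so there is no figure of the plan's own to reproduce. **Assumed throughout:** 8 per arm, 4 per arm-by-activation cell unless stated, no dropout, two-sided 5% (upper 2.5% tail for the directional correlations), and shifts in units of the within-arm SD of change.

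**1. Hypothesis 3 with random effects of subject and item only.** Take m items, 50% accuracy and a between-participant SD of true change s. The variance of one participant's observed change is s² + 2(0.25)/m, whereas the model allows about 2(0.25)/m. With k the ratio of the two, the type I error is about 2[1 − Φ(1.96/√k)].

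| m | s | k | Type I error |
|---|---|---|---|
| 40 | 0.05 | 0.0150/0.0125 = 1.20 | 7% |
| 40 | 0.10 | 0.0225/0.0125 = 1.80 | 14% |
| 175 | 0.05 | 0.00536/0.00286 = 1.875 | 15% |
| 175 | 0.10 | 0.01286/0.00286 = 4.50 | 36% |

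Adding the activation category does not repair this. With m = 175, s = 0.05 and a category–change correlation of 0.5, the error is 12.8% with or without it.

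**2. Hypothesis 3 with by-subject change modelled.** Simplify to one change score per participant and a 1 SD priming effect. Let r be the correlation of the with/without category with change inside an arm. With the category in the model, the residual SD is √(1 − r²), the noncentrality is √(8×8/16)/√(1 − r²) = 2/√(1 − r²), and the error df is 13. At r = 0.5 that is 2/0.866 = 2.31, giving 57%. The unadjusted figures come from simulation.

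| r in A / B | Power without category | Power with category |
|---|---|---|
| 0 / 0 | 46% | 46% |
| 0.3 / 0.3 | 45% | 49% |
| 0.5 / 0.5 | 44% | 57% |
| 0.6 / 0 | 45% | 48% |

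At r = 0.5 in both arms, the unadjusted type I error is about 2.4% against a nominal 5%. A three-session, 2-df test, with correlation 0.8 between the two change scores, gives 36 vs 40% at r = 0.3 and 33 vs 47% at r = 0.5.

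**3. Cost when the cells are uneven.** With a 5/3 versus 3/5 split, the group–category correlation is (25 − 9)/64 = 0.25. The noncentrality falls to 2√(1 − 0.0625) = 1.94, and adjusted power at r = 0 is 43% against 46% unadjusted.

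**4. Hypothesis 1.** Let the arms differ by d₁ SD in naming change and d₂ SD in imaging change, with no association inside either arm. The pooled population correlation is (d₁d₂/4)/√[(1 + d₁²/4)(1 + d₂²/4)]. At d₁ = d₂ = 1 this is 0.25/1.25 = 0.20.

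| d₁ / d₂ | Pooled r | Pooled test positive | Given group |
|---|---|---|---|
| 0.5 / 0.5 | 0.06 | 4.1% | 2.5% |
| 1 / 0.5 | 0.11 | 6.1% | 2.5% |
| 1 / 1 | 0.20 | 11.6% | 2.5% |
| 1.5 / 1.5 | 0.36 | 30% | 2.5% |

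The price of including group is one df (14 to 13). At a true r of 0.5 with no arm shift, power is 53% pooled and 50% given group.

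**5. Hypothesis 2.** Because the arms are balanced on activation, group is not expected to confound activation with change. With a 1 SD arm shift the pooled test is slightly conservative (1.8% against 2.5%). At slopes of 0.6 in both arms, power is 62% pooled and 74% with group. At a 0.5 SD shift the gain is only 1–2 points.

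**The case against.** - **The C2.1 list may be incomplete.** This stands. The group-by-session interaction is itself missing from C2.1 and appears only in C2.2. A reader might infer that the plan excludes the activation factor. The text supports only that it does not name it.
- **On the model as named, the missing factor is not the main problem.** This also stands. A reader might infer that omitting the factor biases Hypothesis 3 or invites false positives. It does neither when balance is achieved. The anti-conservative error comes from the missing by-subject session effect, which the plan permits but does not require.
- **The gains assume a strong factor.** Fair. An r of 0.5 with the category means that the strata differ by 2(0.5)/√0.75 = 1.15 within-stratum SDs in change. If r is instead with continuous activation and the adjustment uses a median split, adjusted power is about 48% at 0.3 and 52% at 0.5. If priming evens out baseline excitability, as its rationale in A.3.1 makes plausible, the gain is about 3 points.
- **Sixteen participants cannot carry many terms.** Partly fair. The costs above come from linear models of change scores. The item-level multilevel model with the added terms was not tested.
- **The Hypothesis 1 tail rates are not type I error for the stated correlation.** Correct. When priming shifts both measures, the pooled correlation truly is not zero. The rates are errors only for the narrower claim of association within arms. Nothing in the documents shows that imaging would shift by 1 SD, and group is examined separately in the second-level imaging analysis. Whether the between-arm part should count depends on the hypotheses, which are not in the available text.

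**Conclusion.** The gap in C2.1 is real and worth closing. With only subject and item random effects, the Hypothesis 3 test rejects too often if participants differ in change: about 7–36% under the assumed item counts and SDs. With by-subject change modelled, leaving out the balancing factor makes the test conservative. It then costs from nothing (r = 0) to about 13 points of power (r = 0.5 with the category in both arms) at a 1 SD effect.

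For Hypothesis 1, the pooled correlation can reflect the arm contrast alone. This is material when priming shifts both measures by about 1 SD or more and slight at 0.5 SD. It is a question of interpretation that a group-adjusted test would settle, not a demonstrated false-positive rate.

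A reader might also infer that Hypothesis 2 is defective without group. It is not: type I error is not inflated, and the point is one of efficiency.

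Every size here rests on assumed arm sizes, cell sizes, item counts, slopes and shifts. Confidence is medium.

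**What to change.** **C2.1.** State the full model: session, group and group by session; a by-subject random session effect as a requirement; and the with/without RH PTr activation category used at allocation, with its interaction with session. In the three-session model the category adds three fixed terms (one main effect and two session contrasts). If activation is unrelated to change, this costs 0–3 points of Hypothesis 3 power, depending on how evenly the cells fill. It is a heavier model for 16 participants, so a simpler fallback should be named in case it does not converge.

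**H1a/H1b.** Also test each correlation with group as a covariate (partial correlation or regression), and say in advance whether between-arm variation counts as support. Cost: one degree of freedom, about 3 points of power at a true r of 0.5.

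**H2a/H2b (optional).** Include group as a covariate and name the primary test in advance. Cost: about 1 point if priming shifts nothing. No preference over a Group A-only test is offered, because that depends on whether priming removes the slope in Group B: at slopes 0.6/0 with a 1 SD shift, power is 22% group-adjusted and 40% in Group A alone.

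All of this is wording in the analysis plan. No new data are needed.

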from a single session of inhibitory rTMS are transient, studies in which RH PTR has been targeted across repeated sessions have affected naming improvements that accrue over time and persist after the termination of rTMS administration [30-31]. These longer-lasting changes in the dynamics of the language network are possibly a consequence of mechanism changes in the effectiveness of synapses between cortical neurons, similar to long term depression/potential [32]. Thus, language use even outside of the direct context of the rTMS session serves to reinforce the more functional LH-focused language network and consequently, to discourage recruitment of the maladaptive RH one [28]. This view is further supported by the observation that improvements in language measures continue significantly *beyond* the conclusion of rTMS administration, up to several years [33].

A3. Potential sources of response variability to rTMS

A.3.1 Baseline cortical excitability

Despite the strong positive evidence for the effectiveness of inhibitory rTMS to RH PTR to improve naming in chronic aphasia, not every individual responds significantly [34]. One potential explanation for this finding is that the effect of 1Hz rTMS is state dependent. That is, it has a stronger inhibitory effect when administered to a brain region that has a higher level of excitability [35]. For example, the inhibitory effect of 1 Hz rTMS is *stronger and lasts longer* when participants move their hand prior to rTMS stimulation of the portion of the motor cortex containing the representation of the hand. Perhaps more importantly, inhibitory rTMS has been found to have a paradoxical *excitatory* effect when applied to brain regions already in a state of inhibition [36].

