Study timeline: Average estimated participant enrollment length is 10-14 weeks including follow-up, therefore participant recruitment will conclude 4 months prior to last planned data collection. Planned enrollment will be 6 participants in Year 1 and 10 in Year 2. The accelerated enrollment will be made possible in Year 2 due to the proposed hiring of an additional 5/8 staff speech-language pathologist who will assist with participant recruitment, assessment, analyses, and manuscript preparation. Further, as ASPRR has a current enrollment of 133 individuals with aphasia (84 Veterans), and the VAPHS clinical service has historically received approximately 8 new outpatient aphasia treatment referrals per quarter, this enrollment target is feasible.

Task	Protocol Preparation and Refinement				Preliminary Analyses and Conference Submission(s)								Analysis and Manuscript Preparation, Preparation of Subsequent Grants (CDA-2, Merit Award)											
	Participant Recruitment																							
	Participant data collection										Year 2 Staff SLP search													
Month	1	2	3	4	5	6	7	8	9	10	11	12	13	14	15	16	17	18	19	20	21	22	23	24

Table 2: Study timeline

Future Directions: If the proposed study is successful, a subsequent Merit Review application will investigate: 1) use of rTMS to augment treatment gains for well-established behavioral interventions; 2) connection of regions modulated by rTMS to prominent neurocognitive models of naming; and 3) relationships between changes in functional (effective) and structural (white matter) brain connectivity. Addressing these goals will both inform theoretical understanding of aphasia recovery and bring rTMS closer to direct clinical applicability.

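### Hypothesis 3 compares 16 participants, but C2.1 leaves the by-subject session effect optional; if it is omitted and participants differ in change, type I error exceeds 5%

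*Combined protocol and SAP*

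**What the plan says.** C2.1 takes item-level PNT performance as the data for treatment effects by group. On the model it says "Accuracy data will be analyzed using multilevel linear or logistic regression in R" and "Models will include fixed effects of session (baseline, post-treatment, follow-up), and group (Group A, Group B) and random effects of subject and item". It then adds "Analyses may include additional random-effects structure if needed to improve model fit". It names no fit criterion, no by-subject session effect and no reference distribution for the tests.

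The last paragraph of C2.2 sets the rule for Hypothesis 3: "A significant interaction of group and session (analysis C2.1", with the direction given as "suggesting that Group B receiving the 6 Hz primed inhibitory rTMS showed greater naming improvement across time will support Hypothesis 3".

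C.1 Procedures assigns each participant to one group and balances on one factor: "an equal number of participants with and without baseline RH PTr activation will be approximated in each group". The study timeline gives the size: "Planned enrollment will be 6 participants in Year 1 and 10 in Year 2", so 6 + 10 = 16.

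The text between the heading of section B and the methods paragraphs just before C.1 was not available. A statement there on sample size or on the hypotheses cannot be excluded.

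**The concern.** Group varies between participants, not between items. The yardstick for group by session is therefore how much participants differ in their change over time. A model with only a subject intercept and an item intercept has no term for that variation. It treats many items named by one person as independent evidence about priming, so the standard error is too small.

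The protocol expects such variation. Section A calls treatment response highly variable. A.3.1 says "not every individual responds significantly" and expects little benefit in people who keep left PTr function. The summary closing A.3.2 lists the sources of response variability as something still to be understood.

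At stake is a claim that 6 Hz priming improves naming when a few Group B participants simply changed more than others. About half of the false rejections would favour Group B.

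**Working it through.** The available text gives no power, SD or effect size, so there is no figure of the plan's own to reproduce.

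**Inputs.** From the documents: 16 participants, three sessions, item-level accuracy, assignment by participant. Assumed, not in the documents: 8 per group; two-sided 5%; 60 or 175 PNT items (m); subject SD 1.2 and item SD 1.0 logit; mean logit 0; no dropout; true group-by-session effect zero; SD of true individual change between two sessions (τ) 0.1 to 0.5 logit.

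**1. Closed form, post-treatment minus baseline, intercepts only.** With accuracy p, the true variance of the contrast exceeds the modelled variance by

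R = 1 + τ²·m·p(1−p)/2, and type I error = 2·[1 − Φ(1.96/√R)].

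- τ = 0: R = 1, error 5.0%.
- m = 60, p = 0.5, τ = 0.3: R = 1 + 0.09×60×0.25/2 = 1.675, error 13.0%.
- m = 175, p = 0.5, τ = 0.5: R = 1 + 0.25×175×0.25/2 = 6.469, error 44.1%.

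Any τ above 0 gives an error above 5%, and it grows with the number of items.

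**2. Simulated 2-df interaction test, linear form, effect omitted.** Two patterns of change were used. *Independent*: a separate deviation for each participant and session, SD τ/√2. *Shared*: one individual change carried by both post-treatment and follow-up.

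| Pattern | Items | τ = 0.1 | τ = 0.3 | τ = 0.5 |
|---|---|---|---|---|
| Independent (10,000 runs) | 60 | 5.4% | 13.0% | 26.8% |
| Independent (10,000 runs) | 175 | 7.3% | 28.2% | 52.6% |
| Shared (3,000 runs) | 60 | 5.3% | 10.4% | 19.1% |
| Shared (3,000 runs) | 175 | 6.5% | 20.1% | 36.0% |

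At τ = 0 the independent runs gave 4.6% and 4.9%. A repeat gave 6.0–26.6% and 7.4–52.6% (independent), and 19.4% and 37.0% at τ = 0.5 (shared). The logistic form with independent deviations gave 5.2–26.2% and 5.8–54.1%.

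**3. Fit clause used (independent pattern).** Adding the effect only when its own 5% F test is significant gives 5.0–8.0% (2.4–4.2% in favour of Group B, 2.5% nominal). BIC gives 5.1–12.4%. In the logistic form a 5% likelihood-ratio rule gives 5.1–12.8%. Much of that excess comes from ML variances and the chi-square reference, since always including the effect there still gives 4.5–10.3%.

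**4. Balancing on baseline RH PTr activation.** If that factor carried half the variance of change and were exactly balanced (an assumption), omission gives 5.4–16.0% (60 items) or 6.0–36.8% (175 items). The 5% F rule gives 1.3–5.7%.

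**5. Candidate replacements.**
- Participant-level t test, mean of post-treatment and follow-up minus baseline, 14 df: 4.2–5.0% (independent) and 4.2–5.7% (shared). With the balancing of step 4 it falls to 0.8–4.8%; with the factor as covariate (13 df) it returns to 4.5–5.3%.
- One common subject-by-session variance with F(2,28): 4.5–5.1% (independent), but 5.1–6.4% (shared). In the limit where all variation lies in one contrast, the statistic follows F(1,14), and P(F(1,14) > 3.34, the F(2,28) cutoff) = 8.9%.
- Same model, large-sample chi-square: P(2·F(2,28) > 5.991) = 6.6%, or about 9.0% with the ML variance (28/32 of the unbiased one).

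**The case against.** The strongest reply is that the plan already provides for this. C2.1 allows more random effects where fit requires them, and the largest errors arise where a check would hardly miss the effect: at 175 items it is selected in 94–100% of trials at τ = 0.3 to 0.5. A reader might infer that the plan commits to an intercept-only model and so carries a false-positive rate near 50%. The documents do not support that. Random effects of subject do not exclude a session effect by subject, the top figures need the fit clause to go unused, and they fall by about a third if change persists to follow-up, which A2 describes for repeated sessions.

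That limits the size but does not remove the point. The clause is permissive and has no criterion. At 60 items and τ = 0.3 a 5% check selects the effect in only 47% of trials, and the resulting error depends on which rule the analyst picks later.

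A reader might also infer that the interaction is absent from the analysis, because C2.1 does not list it. The rule in C2.2 attributes it to C2.1, so this needs only clarification, as does the choice between linear and logistic.

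Two further objections stand. Balancing on baseline activation may remove much of the excess once a fit check is used. And item count, SDs, allocation and alpha are assumed, so the magnitudes are less certain than the direction; at 60 items and τ = 0.1 the excess is about 1 point or less.

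**Conclusion.** The concern holds in conditional form and should be fixed. If participants differ in change and the by-subject session effect is omitted, type I error for Hypothesis 3 exceeds 5%, whatever the exact inputs. Under the assumptions above it is about 6–27% (60 items) or 7–53% (175 items) with independent session deviations, and about 6–19% or 7–37% with shared change. With the fit clause applied as a 5% F test in the linear form, the excess is small (about 5–8%), and smaller still if balancing on baseline activation accounts for part of the variation. The defect is that the error rate of the only stated rule for Hypothesis 3 rests on an optional, undefined choice.

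**What to change.** In C2.1, name one decisive test of Hypothesis 3: a participant-level comparison of one stated PNT change score, for example the mean of post-treatment and follow-up minus baseline, by t test with 14 df, or 13 df with baseline RH PTr activation as covariate. Without that covariate the test may be conservative. Keep the item-level model as support, with a by-subject random session effect included regardless of fit.

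If the item-level model is to decide, include by-subject random effects for the stated change contrast, not only one common subject-by-session variance, and test that single contrast with about 14 denominator df. Do not use a large-sample chi-square, or F(2,28) with sphericity left unstated. In either case list group by session in C2.1, choose the linear or logistic scale, and align the Hypothesis 3 rule in C2.2 with the chosen test.

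The cost is a few sentences and a line or two of code, with no new data or visits. The standard error for Hypothesis 3 widens by a factor of about 1.0–1.5 (60 items) or 1.1–2.2 (175 items) over τ = 0.1 to 0.5. One contrast replaces the 2-df interaction, so a difference confined to one of the two later sessions would be diluted.
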